4.5.8 Dermatologic Examinations

Full-body dermatologic examinations should be performed at regular intervals as outlined in the schedule of assessments (see [Appendix 1](#)). A dermatologist should be consulted for patients who develop Grade ≥ 3 skin disorders or any grade rash with concurrent signs or symptoms strongly suggestive of a severe Type I hypersensitivity or anaphylactic or anaphylactoid reaction, with painful desquamation or mucosal

involvement suggestive of Stevens-Johnson syndrome or toxic epidermal necrolysis, or with other life-threatening complications.

4.5.9 Laboratory, Biomarker, and Other Biological Samples

Assessments that require blood, draws should be monitored closely to ensure that no more than 2.5% of the total blood volume is taken at one time or that no more than 5% of the total blood volume is taken over a 30-day period (total blood volume is defined as 80 mL/kg). Institutions should use micro sampling systems to minimize the amount of blood drawn when able. In situations where the total amount will exceed the amount stated above, clinical laboratory assessments should be prioritized. Any remaining blood should be sent for PK analysis followed by biomarker and PD analyses.

Samples for the following laboratory tests will be sent to the study site's local laboratory for analysis:

- Hematology (WBC count, hemoglobin, platelet count, 3-cell differential count [absolute neutrophils, monocytes, and lymphocytes])
- Serum chemistry (sodium, potassium, magnesium, chloride, bicarbonate (or total carbon dioxide), glucose, BUN or urea, creatinine, total protein, albumin, phosphorus, calcium, total bilirubin [if abnormal, fractionate sample for direct and indirect], alkaline phosphatase, CPK, ALT, AST, uric acid, LDH)
- Urinalysis (specific gravity, glucose, protein, blood) in children > 3 years of age.
Creatinine clearance as clinically indicated (If radioisotope glomerular filtration rate is routinely performed at the institution to measure patients' creatinine clearance, this test can be used to assess renal function at screening, per the eligibility criteria. Otherwise, serum creatinine is sufficient to document renal function at screening).
- Pregnancy test
All post-menarcheal females will undergo pregnancy tests within 1 week prior to the start of each treatment cycle. A serum pregnancy test must be performed at screening (prior to Cycle 1). Urine or serum pregnancy tests will be performed prior to all subsequent cycles.
- Coagulation (INR, aPTT, PT)

Samples for the following research laboratory tests will be sent to one or several central laboratories for analysis:

- Plasma samples for PK analysis (see Central Laboratory Manual)

The following samples will be sent to a central laboratory, the Sponsor, or a designee for analysis:

- Plasma samples for exploratory research on candidate biomarkers, including but not limited to *BRAF* mutations, *BRAF* fusions, *RAS* mutations, *NF1*, and other candidate biomarkers (including somatic mutations of the tumor)

- Availability of tumor tissue at study enrollment is mandatory. Archival and/or fresh primary tumor tissue samples are required for exploratory research on candidate biomarkers, including but not limited to p-MEK, p-ERK, Ki67, *BRAF* mutations, *BRAF* fusions, *RAS* mutations, and *NF1*.

Submission of bone biopsy specimens is strongly discouraged due to complications in the assessment of such tissue, but they may be submitted if no other tissue is available.

For patients with archival samples: Representative formalin-fixed paraffin-embedded (FFPE) tumor specimens in paraffin blocks or at least 15 freshly cut, unstained, serial slides (blocks preferred), with an associated pathology report, are required for study entry. The specimen should be of good tissue quality and to have sufficient viable tumor content as determined by the institutional pathologist. Patients with fewer than 15 slides available may be eligible for study entry following discussion with the Medical Monitor. The tumor specimen and associated pathology report must be confirmed to be available prior to patient participation in any study-specific screening procedures and must be shipped within 30 days of first dosing.

- Patients will be encouraged to submit all available FFPE tumor specimens from prior surgeries and biopsies performed as part of routine medical care. If a patient has multiple archival specimens available but only wishes to submit one sample, the specimen obtained closest to the start of treatment should be used, with the exception that non-bone specimens are preferred over bone biopsy specimens.

Archival tumor blocks will be returned to the sites at the end of the study or upon site request.

- Patients without archival samples must be willing to undergo a core or excisional biopsy prior to enrollment. Fine-needle aspiration, brush biopsy, and lavage samples are not acceptable.
- A whole blood sample for molecular analysis of mutations and single-nucleotide polymorphisms (SNPs) is required ONLY for patients who consent to submitting optional on-study tissue (tissue submission described in Section 4.5.10). This sample may be used for the analysis of novel mutations detected in tumor tissue in order to verify the somatic nature of this mutation and SNPs that might be associated with safety, efficacy, or PK of the drug. This sample is not collected if patients have not consented to the optional on-study biopsy.

For sampling procedures, storage conditions, and shipment instructions, see the laboratory manual.

These samples will be destroyed when the final clinical study report has been completed, with the following exception:

- Any remaining samples collected for PK analysis, biomarker assays, and ATA assays may be used for exploratory biomarker profiling, identification, and PD assay development purposes and for additional safety assessments (e.g., ATA assay) as appropriate. The remainder of samples obtained for study-related procedures will be destroyed no later than 5 years after the date of final closure of the clinical database unless the patient gives specific consent for the remainder of the samples to be stored for optional exploratory research. If the patient provides consent for optional exploratory research, the samples will be destroyed no later than 15 years after the date of final closure of the clinical database.

When a patient withdraws from the study, samples collected prior to the date of withdrawal may still be analyzed, unless the patient specifically requests that the samples be destroyed or local laws require destruction of the samples. However, if samples have been tested prior to withdrawal, results from those tests will remain as part of the overall research data.

4.5.10 Acceptability Survey

To better understand the acceptability of the cobimetinib formulations, a survey will be administered immediately following administration of cobimetinib on Day 8 of Cycle 1. It would be advisable that patients rinse their mouths prior to taking the medication and complete the survey before any rinsing or water.

For patients who have not yet developed the cognitive ability to provide detailed feedback on the acceptability of a medication, the parent or guardian will complete the Acceptability Survey based on their observation of their child's reaction and facial expression following the medication intake. Patients able to provide feedback will complete the survey with reading support from their parents or the clinical staff as needed. Study staff and patient's caregiver possibly present during the assessment should remain neutral. If a patient is having difficulty with selecting a score, patients may be asked the interview question first and then redirected to complete the assessment score. Parents or caregivers will be asked about their ease of experience of administering the suspension at home.

The survey will document specific aspects of the acceptability of each of the cobimetinib formulations, including swallowability and palatability (Kozarewicz 2014). The survey is required regardless of whether the patient is taking tablets or suspension.

4.5.11 Samples for Roche Clinical Repository

4.5.11.1 Overview of the Roche Clinical Repository

The Roche Clinical Repository (RCR) is a centrally administered group of facilities used for the long-term storage of human biologic specimens, including body fluids, solid tissues, and derivatives thereof (e.g., DNA, RNA, proteins, peptides). The collection and

analysis of RCR specimens will facilitate the rational design of new pharmaceutical agents and the development of diagnostic tests, which may allow for individualized drug therapy for patients in the future.

Specimens for the RCR will be collected from patients who give specific consent to participate in this optional research. RCR specimens will be used to achieve the following objectives:

- To study the association of biomarkers with efficacy, adverse events, or disease progression
- To increase knowledge and understanding of disease biology
- To study drug response, including drug effects and the processes of drug absorption and disposition
- To develop biomarker or diagnostic assays and establish the performance characteristics of these assays

4.5.11.2 Approval by the Institutional Review Board or Ethics Committee

Collection and submission of biological samples to the RCR is contingent upon the review and approval of the exploratory research and the RCR portion of the Informed Consent Form by each site's Institutional Review Board (IRB) or Ethics Committee (EC) and, if applicable, an appropriate regulatory body. If a site has not been granted approval for RCR sampling, this section of the protocol (Section 4.5.11) will not be applicable at that site.

4.5.11.3 Sample Collection

The following samples will be collected for research purposes, including but not limited to research on dynamic (non-inherited) biomarkers related to cobimetinib or solid tumors:

- Fresh tissue from on-study biopsies and residual tissue from non-study related procedures, from the primary tumor location, metastatic site, or site of local recurrence or advancement will be collected for analyses that may include DNA or RNA extraction. Samples should be obtained at the following timepoints: prior to drug initiation; during the week before Cycle 3 of drug; and at the time of disease progression (if applicable). Patients may choose to consent to any or all of these timepoints.

For fresh tissue biopsies, a minimum of three fresh tissue cores should be acquired using an 18-gauge needle. If not feasible, one or two cores may be acceptable after discussion with the Medical Monitor.

Patients consenting to the optional on-study biopsies will also be required to provide a mandatory whole blood sample listed under the main informed consent form.

For all samples, dates of consent should be recorded on the associated RCR page of the eCRF. For sampling procedures, storage conditions, and shipment instructions, see the laboratory manual.

RCR specimens will be destroyed no later than 15 years after the date of final closure of the associated clinical database. The RCR storage period will be in accordance with the IRB/EC-approved Informed Consent Form and applicable laws (e.g., health authority requirements).

The dynamic biomarker specimens will be subject to the confidentiality standards described in Section 8.4.

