- Of the 58 cell lines assessed, 18 cell lines exhibited RAS/RAF/MEK/ERK pathway activation as defined by oncogenic mutations in NRAS, KRAS, HRAS, or BRAF, by FLT3 internal tandem duplication, or by NF1 homozygous deletion. Of the 18 cell lines with known RAS/RAF/MEK/ERK activation, 9 (50%) cell lines showed sensitivity to cobimetinib with an IC₅₀ of < 0.3 μM, whereas only 4 (10%) of 40 cell lines without these mutations showed sensitivity at this level.
- Responses were observed in cell lines with activating RAS mutations from diseases that do not ordinarily carry RAS mutations. The osteosarcoma cell line 143B, a cell line transformed by murine sarcoma virus encoding a homolog of human KRAS, demonstrated IC₅₀ of 0.351 μM, but significantly less effect was noted in other osteosarcoma lines. The medulloblastoma cell line ONS-76 with an activating NRAS Q61R mutation (Gajjar et al. 2014; Barretina et al. 2012) responded to cobimetinib with IC₅₀ of 0.074 μM.

Several MEK-inhibitors have shown efficacy in in vivo mouse models of pediatric cancers (see Section 1.1). Additionally, cobimetinib has now been evaluated in a neuroblastoma murine xenograft model. Xenografts were derived from SK-N-AS cells, a neuroblastoma cell line with an NRAS Q61K mutation. Cobimetinib was orally administered at multiple doses (1, 3, 5, and 7.5 mg/kg). At the highest tested dose, cobimetinib inhibited tumor growth by 49% (as measured by area under the concentration-time curve [AUC]/day) relative to vehicle, and the time to progression (to five times the initial tumor size) increased from 6.5 days to 11.5 days. ERK phosphorylation was reduced in murine tumors after cobimetinib dose administration; an effect was observed within 2 hours after cobimetinib dosing, and maximal effect was observed at 8 hours post-dosing (Genentech, Inc., unpublished results).

In summary, inhibition of the RAS/RAF/MEK/ERK pathway has been observed with several MEK small molecule inhibitors including cobimetinib. This activity was observed across a spectrum of pediatric tumors in vitro, mainly in RAS pathway activated tumor types, and in vivo in a RAS-mutant neuroblastoma xenograft model.

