3.4.4 Exploratory Outcome Measures

The exploratory outcome measures for this study are as follows:

- Levels of potential PD biomarkers (potentially including, but not limited to, p-MEK, p-ERK, and Ki67) measured in tumor tissue collected at baseline, on treatment, and at the time of disease progression

- Correlation between non-inherited and inherited biomarkers in plasma (potentially including, but not limited to, *BRAF* mutations, *BRAF* fusions, *RAS* mutations, and *NF1* alterations) with safety, PK, or efficacy outcome measures
- To explore potential relationships between cobimetinib PK and other outcome measures (such as safety or efficacy outcome measures)
- ORR for LGG, defined as the percentage of patients with measurable disease who have a complete or partial response on two consecutive occasions ≥ 4 weeks apart, as determined by the investigator using RECIST v1.1
- Modified ORR for LGG, defined as the percentage of patients with measurable disease who have a complete, partial, or minor response on two consecutive occasions ≥ 4 weeks apart, as determined by the investigator using the RANO criteria for LGG (see [Appendix 5](#)).
- Diffusion activity in tumors before and after cobimetinib treatment, as demonstrated on available MRI scans
- Metabolic activity in tumors before and after cobimetinib treatment, as demonstrated on available PET scans
- Acceptability survey

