4.3.2 Dosage, Administration, and Compliance

Cobimetinib will be taken orally once daily on Days 1–21 of each 28-day treatment cycle (21/7 dosing schedule) according to the guidance provided in [Appendix 10](#) until the occurrence of disease progression as determined by the investigator, death, unacceptable toxicity, or patient or investigator decision to discontinue treatment. The starting dose for tablets will be 0.6 mg/kg in the dose-escalation stage. Possible subsequent doses are listed in Section 3.1.1.2. Pediatric patients (< 18 years of age) enrolled in the expansion stage will be treated at or below the MTD or MAD, as determined by the Sponsor. Adult patients (≥ 18 years of age) enrolled in the expansion stage will be treated with the adult recommended dose of 60 mg daily. In case a de-escalation is required in these adult patients, please refer to Section 5.1.1. Patients who reach 18 years of age after starting study therapy will remain on weight-based dosing. Patients will be weighed at the beginning of each cycle. In Cycle 1, weight recorded during the screening period is acceptable. For subsequent cycles, weight must be recorded within 3 days prior to the Day 1 dose, and the dose will be adjusted as needed. No patients will be treated with cobimetinib on Days 22–28 of each cycle.

Patients under 6 years of age or weighing <20 kg are only eligible to receive the drug in suspension (see Section 3.3.1.1 for rationale). Once the suspension is available, the Sponsor will determine whether tablets will remain available to sites based on the observed safety profile and PK of the two formulations, as well as operational feasibility of providing two formulations. If a patient is eligible for treatment with either tablet or suspension formulation, and both formulations are available, the investigator will determine the most appropriate formulation for the patient and enroll the patient into study accordingly. However, patients may not switch formulations after the start of therapy unless safety differences between the two formulations mandate a change for all patients on the study.

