Appendix 1 Schedule of Assessments (cont.)

	Screening ^a	Treatment Period									Follow-Up Period	
	Day	Cycle 1						Cycle 2	Cycle 3	Cycles 4+	Study Drug Discont. ^b	Long-Term Follow-Up ^c
		-28 to -1	1	2	8	15	21	22	1	1		
Window (days)			0	±3	±3	±3	^v	±3	±3	±3	±3	±14 Yr 1, then ±30
Concomitant medications	x ^w	x ^w		x	x	x		x	x	x	x ^w	
Adverse events	x	x		x	x	x		x	x	x	x	
Cobimetinib administration		x ^x	x ^x	x ^x	x ^x	x ^x		x ^x	x ^x	x ^x		
Study drug compliance				x	x	x		x	x	x	x	
Acceptability survey				x ^y								
12-lead ECG	x											
Echocardiogram	x							x ^z		x ^z	x	
Ophthalmologic examination ^{aa}	x			x ^{bb}	x ^{bb}			x ^{bb}	x ^{bb}	x ^{bb}	x ^{cc}	
Dermatologic examination (full body)	x							x ^{dd}		x ^{dd}		x
Survival assessment												x
Optional RCR tumor tissue sample ^{ee}		x						x			x	
Blood sample for molecular analysis ^{ff}		x										

CT = computed tomography; discont. = discontinuation; eCRF = electronic Case Report Form; MRI = magnetic resonance imaging; OCT = optical coherence tomography; PK = pharmacokinetic; RCR = Roche Clinical Repository.

Notes: All assessments should be performed within 3 days of the scheduled visit (excluding Day 1 of Cycle 1), unless otherwise specified. On treatment days, all assessments should be performed prior to dosing, unless otherwise specified. Cycles are 28 days in length.

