Appendix 1 Schedule of Assessments (cont.)

progression as determined by the investigator, death, unacceptable toxicity, or patient or investigator decision to discontinue treatment. Patients will be weighed at the beginning of each cycle, and the dose will be adjusted as needed.

^y Performed immediately after dosing (Appendix 9).

^z Echocardiograms should be performed at Cycle 2 and every third cycle thereafter (i.e., Cycles 5, 8, 11, etc.)

^{aa} Ophthalmologic examinations will include age-specific visual acuity testing (*should be reported in Snellen units*), intraocular pressure measurements, slit-lamp ophthalmoscopy, and spectral domain OCT at all scheduled timepoints. Indirect ophthalmoscopy and color fundus photography will be performed at screening and (if performed) at study drug discontinuation. If spectral domain OCT is not available, time-domain OCT may be performed. In patients who are unable to successfully complete OCT scans due to underlying visual impairment from non-retinal causes (such as brain tumor), color fundus photography and indirect ophthalmoscopy should be performed instead of OCT at each scheduled ophthalmologic evaluation. Fluorescein angiography will be performed for identified OCT serous fluid accumulation or edema and thereafter based upon clinical findings. Binocular indirect ophthalmoscopy will be performed any time fluorescein angiography is performed.

^{bb} During treatment, ophthalmologic examinations should be performed on Cycle 1 Days 8 and 15 and at the start of every subsequent cycle; *for patients who have completed 6 cycles of cobimetinib therapy and who have not developed serous retinopathy, retinal detachment, or other adverse events involving the retina, ophthalmologic evaluations will be performed at Cycles 8, 10, 12, 16, 20, 24, and every 6 cycles thereafter.*

^{cc} Ophthalmologic examination is not required if performed within the previous 12 weeks and there were no clinically significant findings or changes identified in the prior examination.

^{dd} During treatment, dermatologic examinations will be performed at Cycle 2 and every third cycle thereafter (i.e., Cycles 5, 8, 11, etc.).

^{ee} Optional RCR tumor tissue samples will be collected prior to drug initiation, during the last week of Cycle 2 (i.e., prior to the start of treatment in Cycle 3) and at the time of disease progression or treatment discontinuation. Samples may be collected at the time of scheduled tumor assessments.

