Appendix 2 Schedule of Pharmacokinetic and Pharmacodynamic Assessments

Visit	Timepoint	Sample Type
Cycle 1, Day 1	Prior to the dose	Plasma PK sample for cobimetinib + Plasma PD biomarker sample
	2 hr (\pm 30 min) after the dose	Plasma PK sample for cobimetinib
	4 hr (\pm 30 min) after the dose	Plasma PK sample for cobimetinib
	6 hr (\pm 30 min) after the dose	Plasma PK sample for cobimetinib
	24 hr (\pm 1 hr) after the dose, prior to dose on Day 2 of Cycle 1	Plasma PK sample for cobimetinib
Cycle 1, Day 21	Prior to the dose	Plasma PK sample for cobimetinib
	2 hr (\pm 30 min) after the dose	Plasma PK sample for cobimetinib
	4 hr (\pm 30 min) after the dose	Plasma PK sample for cobimetinib
	6 hr (\pm 30 min) after the dose	Plasma PK sample for cobimetinib
	24 hr (\pm 1 hr) after the dose	Plasma PK sample for cobimetinib
Cycle 2, Day 1	Prior to the dose (within 4 hr prior)	Plasma PK sample for cobimetinib
Cycle 2 (and every 2 cycles thereafter), Days 22–28	Samples should be collected on the day of scheduled tumor assessments.	Plasma PD biomarker sample
Study drug discontinuation	Any time during visit	Plasma PD biomarker sample

hr = hour; min = minute; PD = pharmacodynamics; PK = pharmacokinetic.

Note: Except for Day 1 of Cycle 1, all other study visits and assessments during the treatment period should be performed within 3 days of the scheduled date.

Appendix 3

Modified International Neuroblastoma Response Criteria

Below response assessment is modified from the original INRC publication in 1993.

DEFINITION OF MEASURABLE (EVALUABLE) DISEASE ON CT/MRI SCAN

The presence of at least one lesion that can be accurately measured in at least one dimension with the longest diameter at least 20 mm. With a spiral computed tomography (CT) scan, lesions must be at least 10 mm. The investigator will identify up to 10 measurable target lesions to be followed for response. Note that bone lesions will be considered as non-target lesions for evaluation of CT/magnetic resonance imaging (MRI) response since they will be evaluated with MIBG scans.

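### The mid-study tumor biopsy that the plan calls on treatment is scheduled in the drug-free week of Cycle 2, so p-ERK and p-MEK changes will mix trough and near-washout samples

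*Combined protocol and SAP*

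**What the plan says.** Section 3.4.4 lists pharmacodynamic (PD) biomarkers, with p-MEK, p-ERK and Ki67 as examples, "measured in tumor tissue collected at baseline, on treatment, and at the time of disease progression". Section 6.6.1 repeats these three timepoints and plans to examine how the markers change with exposure to the drug. The first exploratory objective in Section 2.5 is the relation between exposure and PD change.

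Section 4.5.11.3 sets the tissue timepoints: "prior to drug initiation; during the week before Cycle 3 of drug; and at the time of disease progression (if applicable". Footnote ee of Appendix 1 gives the middle one as "during the last week of Cycle 2 (i.e., prior to the start of treatment in Cycle 3". Appendix 1 also states "Cycles are 28 days in length", and Section 4.3.2 states "No patients will be treated with cobimetinib on Days 22–28 of each cycle".

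No other tumor tissue is scheduled between baseline and progression or discontinuation. No section sets a biopsy time relative to the last dose or says how off-drug tissue is to be analyzed.

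**The concern.** A PD marker read as a response to exposure depends on how long after a dose the sample is taken. Here the sample described as on treatment falls entirely within the treatment break, and patients may be biopsied on any day of that week. Time since last dose then varies between patients for reasons unrelated to dose level or clearance.

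If p-ERK is not reduced at that biopsy, there are at least two explanations: the drug did not inhibit the pathway in the tumor, or it did and the pathway recovered during the break. As written, the plan cannot reliably separate them. Some patients, many of them children, would accept an optional needle biopsy partly to answer this question.

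**Working it through.** **Timing.** Cycle 3 Day 1 is Cycle 2 Day 29, so the week before it is Cycle 2 Days 22–28. The last possible dose is on Day 21. Gap = biopsy day − 21, which gives 1, 2, 3, 4, 5, 6 or 7 days.

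The gap is longer on some intermittent tablet schedules. In the example in Section 3.3.1.1, 60 mg a week is given as 20 mg on Days 1, 3 and 5 of the week. In the third week of a cycle the last of these is Day 14 + 5 = 19, so the gap is 22 − 19 = 3 to 28 − 19 = 9 days.

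Appendix 1 allows visits within 3 days of schedule unless otherwise specified. Footnote ee specifies the week, so that allowance does not clearly permit a biopsy on Days 19–21.

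**Reproducing the plan's own figures.** Section 1.2.2.1 gives an adult half-life of 43.6 h, steady state in 8–10 days and 2- to 3-fold accumulation. Assume one compartment and first-order loss:

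- Five half-lives: 5 × 43.6 = 218 h = 9.1 days. The fraction of steady state reached is 1 − 2^(−192/43.6) = 95.3% at day 8 and 1 − 2^(−240/43.6) = 97.8% at day 10. This agrees with the protocol.
- Accumulation: 1/(1 − 2^(−24/43.6)) = 1/(1 − 0.683) = 3.15, marginally above the rounded range.

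**Predicted plasma level at biopsy.** Relative to the ordinary 24-h trough, the level t hours after the last dose is 2^(−(t − 24)/43.6). For a Day 21 dose:

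| Biopsy day | 22 | 23 | 24 | 25 | 26 | 27 | 28 |
|---|---|---|---|---|---|---|---|
| Hours since dose | 24 | 48 | 72 | 96 | 120 | 144 | 168 |
| % of trough | 100 | 68 | 47 | 32 | 22 | 15 | 10 |

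The mean over the seven days is 42%. With a 48 h half-life (Section 3.3.1.1 says approximately 2 days), Day 28 is 12.5% and the mean is 45%. The two extreme days differ about 10-fold in predicted plasma level.

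**Measured exposure near the biopsy.** The last pharmacokinetic (PK) draw in Appendix 2 is before the dose on Cycle 2 Day 1, which is 22 − 1 = 21 to 28 − 1 = 27 days before the biopsy.

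**The case against.** The strongest reply is that plasma is the wrong compartment. Section 1.2.1 reports that drug persisted in xenograft tumors once plasma levels had fallen, and that ERK1 inhibition followed tumor concentration more closely than plasma concentration. Day 22 is no more than an ordinary trough. This stands: the percentages above describe adult plasma, and the fall in the tumor may be smaller.

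A reader might infer from the neuroblastoma xenograft that p-ERK suppression lasts only 2 to 8 hours. The text does not support that. It says "an effect was observed within 2 hours after cobimetinib dosing, and maximal effect was observed at 8 hours post-dosing", which gives onset and time of maximum in one mouse model. It gives no time of recovery and nothing on Ki67.

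A reader might also conclude that the biopsy has no value. That goes too far. Section 4.5.11.3 foresees DNA and RNA work, which the timing does not affect, and residual tissue from non-study procedures could by chance come from a dosing day.

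Nor do the documents show that the plasma samples labelled PD in Appendix 2, drawn in the same week, are mistimed. The plasma markers named in Section 4.5.9 are of the mutation type, and no plasma p-ERK assay is mentioned.

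Finally, exposure is partly covered. Patients record the date and time of each dose in a diary (Section 4.3.2), and Section 6.4 plans a population PK analysis using dosing information. A laboratory manual, not available here, may add timing detail. This makes the problem easier to repair, but nothing in the plan says that these data will be linked to the biopsy.

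**Conclusion.** The inconsistency is real: tissue called on treatment in Sections 3.4.4 and 6.6.1 is scheduled when nobody is dosed. The gap of 1 to 7 days follows from the text for a Day 21 dose, and dose holds or intermittent tablets lengthen it. The range from 100% to about 10% of trough rests on an adult plasma half-life and one-compartment decay.

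Loss of the p-ERK signal in tumor cannot be quantified from the documents. The supportable conclusion is attenuation and added variance in the exposure–PD analysis, together with a null result that could not be reliably distinguished from recovery off drug.

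The consequences are limited. The endpoint is exploratory, the biopsy is optional, and no dose, safety or primary efficacy conclusion depends on it. It is still worth correcting, because the minimum repair needs no extra procedure.

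**What to change.** Reconcile the on-treatment label in Sections 3.4.4 and 6.6.1 (and the synopsis) with the Days 22–28 timing in Section 4.5.11.3 and Appendix 1 footnote ee. There are two ways:

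1. **Preferred.** Move the optional mid-study biopsy to a day late in Cycle 2 on which the patient takes drug, with a stated post-dose window, subject to the sponsor's review of biopsy bleeding risk. Cycle 1 Day 21 is a poor choice although a PK profile is drawn then. It lies in the window for dose-limiting toxicity (DLT), where a hemorrhage of Grade 2 or higher judged at least possibly related counts as a DLT (Sections 3.1.1 and 3.1.1.1).
2. **If the visit is kept.** Label the sample off-drug, record the date and time of biopsy, link it to the last dose in the diary, and state in Section 6.6.1 that PD change will be analyzed by time since last dose or by model-predicted concentration at biopsy.

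Cost: the second option needs a biopsy date and time field and a sentence in the analysis section. The first keeps the number of biopsies unchanged, but the biopsy no longer shares the end-of-Cycle-2 scan visit and is done while the patient is on drug, with hemorrhage an identified risk (Section 5.1.2.1).
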